10.4.1.6 General Physical Examination Findings

At screening, any clinically significant abnormality should be recorded as a pre-existing condition (refer to Section 10.4.1.5). During the study, any new clinically significant findings and/or abnormalities discovered on physical examination that meet the definition of an AE (or an SAE) must be recorded and document as an AE or SAE on the AE eCRF.

10.4.1.7 Hospitalization, Prolonged Hospitalization, or Surgery

Any AE that results in hospitalization or prolonged hospitalization should be documented and reported as an SAE unless specifically instructed otherwise in this protocol (refer to Section 10.1.1.1).

There are some hospitalization scenarios that do not require reporting as an SAE when there is no occurrence of an AE. These scenarios include planned hospitalizations or prolonged hospitalizations to:

- Perform a protocol-mandated procedure or assessment
- Undergo a diagnostic or elective surgical procedure for a pre-existing medical condition that has not changed
- Insert an in-dwelling IV catheter (such as a Port-a-Cath or other brand) for administration of study drug or FVIII replacement therapy.
- Receive scheduled therapy (study drug or otherwise) for the study indication

10.4.1.8 Deaths

All deaths that occur during the AE reporting period (refer to Section 10.3.1), regardless of attribution, will be recorded on the AE eCRF and expeditiously reported to the Sponsor as an SAE.

When recording a death, the event or condition that caused or contributed to the fatal outcome should be recorded as the single medical concept on the eCRF. If the cause of death is unknown and cannot be ascertained at the time of reporting, record "Unexplained Death" or "Death of Unknown Cause" on the AE eCRF.

10.4.1.9 Pregnancy

Although not an AE per se, pregnancy in the partner of a subject taking trial medication should be reported expeditiously to the Sponsor to facilitate outcome monitoring by the Proprietary and Confidential 24 August 2021

270-201 Amendment 10

Sponsor. Pregnancy in partner should be reported during the period up to 5 years after viral infusion.

Pregnancy in a partner should be reported within 24 hours of the site becoming aware of the pregnancy by entering the information on the Pregnancy eCRF and submitting to BPV within 24 hours of the site becoming aware of the event. The Investigator must make every effort to follow the subject's partner (with that partner's consent) through resolution of the pregnancy (delivery or termination) and to report the resolution on the Pregnancy Follow-up eCRF. In the event of pregnancy in the partner of a study subject, the Investigator should make every reasonable attempt to obtain the woman's consent for release of protected health information.

Abortion, whether therapeutic or spontaneous, should always be classified as an SAE (as the Sponsor considers these to be medically significant), recorded on the AE eCRF, and expeditiously reported to the Sponsor as an SAE.

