At applicable sites, certain study assessments designated in the Schedule of Events may be performed by a mobile nursing (MN) professional at the subject's home or another suitable location, such as their school or office, to improve access and convenience for subjects participating in the study. The Sponsor may select a healthcare company that will be responsible for providing MN services for participating sites (the MN vendor). The MN vendor is responsible for ensuring that all MN professionals are licensed, qualified, and in good standing, as per applicable regulations, and that appropriate background checks have been performed. If the investigator at a participating site determines that MN services are appropriate for a subject and the subject gives written informed consent to participate in MN visits, the MN network will communicate with the subject and the subject's site.

Because subjects develop neutralizing immunity upon exposure to the capsid, re-challenge of vector is not a likely treatment option and these subjects have effectively a single opportunity for therapy using this AAV capsid. Efficacy will be determined by FVIII activity at 16 weeks post dose. Safety will be evaluated for approximately 7 years after dosing. Any safety signal may trigger a review of the data and possible additional immunogenicity studies that include an assessment of cellular immune responses using collected PBMC. Additionally, if any of the events listed in Section 9.3.4.1 occur, enrollment into the trial will be halted to complete an extensive safety analysis. Notification of the study enrollment halt will be sent by the Sponsor to the participating sites via telephone and email immediately after becoming aware of a safety concern. This will ensure no additional subjects are dosed until the signal has been completely evaluated. If, following safety review by the DRB and the Sponsor, it is deemed

BOMARIN

270-201 Amendment 10

appropriate to restart dosing, a request to restart dosing with pertinent data will be submitted to the health authority.

A summary of events and assessments are provided by visit in Table 9.1.1 for Screening, Baseline and BMN 270 Infusion, in Table 9.1.2 for Post-Infusion Follow-up, and in Table 9.1.3, Table 9.1.4, and Table 9.1.5 for Safety Follow-up.

Table 9.1.6, dealing with reactive corticosteroid use in the event of elevated LTs, is discussed in Section 9.4.8.2.

Liver Biopsy Substudy Design

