^d Includes hFVIII activity level (one-stage clotting and chromogenic substrate assay), Bethesda assay (with Nijmegen modification) for hFVIII inhibitor level, and hFVIII coagulation activity exploratory assay. If a subject has used FVIII within 72 hours of a measurement day, all efforts should be made to obtain FVIII activity

Proprietary and Confidential

24 August 2021

BOMARIN Page 51 270-201 Amendment 10

measurements when a 72 hour interval without FVIII use is achieved; the 72-hour wash-out period is only intended for subjects who have achieved FVIII \geq 5 IU/dL at 16 weeks after BMN 270 infusion and who have not resumed standard of care FVIII replacement therapy. If FVIII levels are elevated or stable over the course of several weeks, assessment of FVIII activity may be adjusted based on discussion between the Medical Monitor and the Investigator. A d-dimer may be considered under circumstances in which FVIII activity levels are above the normal physiological range and/or if there is a concern for a venous thromboembolism. If a subject tests positive in the Bethesda assay (with Nijmegen modification) in Years 3-5, a fresh sample should be collected within 4 weeks of the initial visit that had a positive result.

- ^e Sample testing during Safety Follow-Up is not required if at least 3 consecutive samples are cleared during the Post-Infusion Follow-Up period. Subjects who have not had 3 consecutive negative semen samples by Week 52 should continue to have PCR testing every 4 weeks (during Year 2), every 6 weeks (during Years 3-5), and/or every 26 weeks (during Years 6-7) until 3 consecutive samples below the limit of detection are documented (or upon consultation between the Investigator and Medical Monitor).
- ^fHaemo-QoL-A QoL assessment during Years 2-5 of Safety Follow-up should be performed at the second Q12W visit each year and at every End of Year visit. During Years 6-7, the Haemo-QoL-A assessment should be performed at the Q26W visits and the End of Year visits.

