9.3.6 Duration of Subject Participation

The duration of this study will be approximately 368 weeks. This includes 4 weeks of screening, 1 day of BMN 270 infusion, 16 weeks of Post-Infusion Follow-Up, and 348 weeks of Safety Follow-Up. A primary endpoint analysis on safety and efficacy will be performed at 16 weeks.

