9.7.9.7 Vector Shedding

Vector shedding has been extensively studied in all similar clinical trials performed to date. (Nathwani 2014; Manno 2006; Schenk-Braat 2007; Croteau 2004). In the literature referenced above, including Haemophilia B clinical studies utilizing AAV2 and AAV8, vector was no longer detectable after 40 days in blood, saliva, urine or stool, but in one study was detected in the seminal fluid but not in motile sperm (Manno 2006). In these studies, the amount of vector present in these bodily fluids involved an extremely small fraction of the infused dose. More recent data from an ongoing AAV-FIX study demonstrates persistence of the vector in both the blood and the semen for at least 39 weeks (Miesbach 2016).

During the Post-Infusion Follow-Up period, subjects will undergo testing of various bodily samples to look for evidence of vector shedding for possible viral transmission. Bodily fluids will be tested by PCR at the time points indicated in Table 9.1.2, Table 9.1.3, Table 9.1.4, and Table 9.1.5. Fluids tested will include:

- Blood
- Saliva
- Semen
- Urine
- Stool

Vector shedding will also be extensively studied in the present clinical trial, every other week between Weeks 4-16, then every 4 weeks to Week 52 until at least 3 consecutive negative results are obtained. Testing of semen will continue through Week 12, even if 3 consecutive negative results have been recorded in that compartment prior to that timepoint. Subjects who have not had 3 consecutive negative semen samples by Week 52 should continue to have PCR testing every 4 weeks (during Year 2), every 6 weeks (during Years 3-5), and every 26 weeks (during Years 6-7) until 3 consecutive semen samples below the limit of detection of the test are documented (or upon consultation between the Investigator and Medical Monitor). Subjects who meet the definition of treatment failure and wish to follow an abbreviated schedule (refer to Section 12.5.3 but who have not cleared vector shedding from semen must still provide samples for assessment until vector shedding has cleared: Proprietary and Confidential 24 August 2021

270-201 Amendment 10

Page 76

every 4 weeks (during Year 2), every 6 weeks (during Years 3-5), or every 26 weeks (during Years 6-7), either by reporting to the site to provide samples or by providing those samples to an MN professional.

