10.3 Methods and Timing for Capturing and Assessing Safety Parameters

10.3.1 Adverse Event Reporting Period

The study AE reporting period is as follows: After informed consent but prior to initiation of study treatment, only SAEs associated with any protocol-imposed interventions will be reported. After informed consent is obtained and the first administration of study drug, the reporting period for all non-serious AEs and SAEs begins and continues for approximately 7 years or until study discontinuation/termination, whichever is longer. The criteria for determining, and the reporting of SAEs is provided in Section 10.1.1.1.

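### Required reporting of partner pregnancies ends at 5 years, two years before AE/SAE reporting, safety follow-up and any outstanding semen vector testing

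*Protocol*

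**What the plan says.** Protocol Section 10.4.1.9 sets the window for partner pregnancies: "Pregnancy in partner should be reported during the period up to 5 years after viral infusion". Within it, the site must notify the sponsor within 24 hours, try to follow the pregnancy to delivery or termination with the partner's consent, and record the result on a dedicated eCRF. The section gives the purpose as outcome monitoring by the sponsor.

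The other safety clocks in the same amendment are longer:

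- Section 10.3.1, on adverse events: "the reporting period for all non-serious AEs and SAEs begins and continues for approximately 7 years or until study discontinuation/termination, whichever is longer".
- Section 9.1: "Safety will be evaluated for approximately 7 years after dosing". Section 12.12 places the last visit at Week 364.
- Section 9.7.9.7, for men whose semen has not cleared: testing continues "every 26 weeks (during Years 6-7) until 3 consecutive semen samples below the limit of detection of the test are documented". Section 12.9.2 drops Year 6-7 testing once clearance is shown by the end of Year 5.

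On the separate inhibitor item, footnote d of Table 9.1.5 (in Section 9.1) says: "If a subject tests positive in the Bethesda assay (with Nijmegen modification) in Years 3-5, a fresh sample should be collected within 4 weeks". Footnote c carries the same limit. Section 12.9.2 keeps the Bethesda assay on the schedule at Weeks 286, 312, 338 and 364.

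**The concern.** Safety is a primary objective, and the protocol treats vector in semen as a real hazard. It governs when contraception may stop (9.3.1, 9.7.9.7), and persistent detection beyond 52 weeks is a criterion for halting enrolment (9.3.4.1). Partner pregnancies are the clinical counterpart of that monitoring, yet their required reporting ends two years before the study does.

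For a pregnancy arising in Year 6 or 7, nothing obliges the site to notify it, seek the partner's consent or establish the outcome. The 13-week remote contacts in those years (12.9.1) collect adverse events, medication changes and diary entries, so they do not prompt the question either. An abnormal outcome could still be reported as an SAE, but the normal outcomes beside it would not be on record.

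**Working it through.** **Inputs**

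- Pregnancy window: 5 years after infusion (10.4.1.9).
- Total duration: "The duration of this study will be approximately 368 weeks", of which 4 weeks are screening, 1 day is infusion, and the rest is "16 weeks of Post-Infusion Follow-Up, and 348 weeks of Safety Follow-Up" (9.3.6).
- End of Year 5: Week 260 (12.8.3). Last visit: Week 364 (12.12).

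**The plan's own duration**

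4 + 16 + 348 = 368 weeks, plus the infusion day. This reproduces the stated figure.

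Post-infusion follow-up is 16 + 348 = 364 weeks = 7 × 52, which matches Week 364.

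**The gap**

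Pregnancy window: 5 × 52 = 260 weeks, the end of Year 5.

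Uncovered: 364 − 260 = 104 weeks, that is, Years 6 and 7.

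Share of post-infusion follow-up: 104 / 364 = 28.6%.

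With the window aligned to Week 364, the gap is 364 − 364 = 0 weeks.

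**What the gap does and does not remove**

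| Item in Years 6-7 | Position under the current text |
|---|---|
| Notification of a partner pregnancy | Not required (10.4.1.9) |
| Follow-up to a normal delivery | Not required (10.4.1.9) |
| Spontaneous or therapeutic abortion | Always an SAE (10.4.1.9), and SAEs are reportable for about 7 years (10.3.1) |
| Congenital anomaly or birth defect | An SAE criterion (10.2), reportable for about 7 years (10.3.1) |
| Anomaly in a later-conceived child, after the study | Sponsor to be told if the investigator learns of it (10.7) |

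**Likely origin**

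The protocol file also contains the earlier amendments. Follow-up was 5 years in Amendment 8, and Amendment 9 extended it to 7. The pregnancy sentence reads 5 years in Amendment 9 and again in Amendment 10. This suggests an update that was missed. The finding does not depend on it, because the mismatch lies wholly within the current text.

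**Inhibitor item**

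Footnotes c and d of Table 9.1.5 tie the 4-week confirmation sample to Years 3-5. The assay is still scheduled four times in Years 6-7, and no corresponding instruction is written for those visits.

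**The case against.** The strongest reply is that the harmful outcomes are still captured. Abortion is an SAE without any year limit, congenital anomaly is an SAE criterion, SAEs are due within 24 hours for about 7 years, and 10.7 reaches beyond the study. That stands. A reader might infer that reproductive-safety data cease at Year 5, and the documents do not support that. What ceases is routine notification and outcome follow-up. A limit on the reply is that a site not told of a pregnancy is less likely to hear of its outcome.

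Second, a reader might infer that partners remain exposed to vector throughout Years 6-7. The text supports this only for men who have not cleared. Semen testing in those years is confined to them, and they may not stop contraception. The protocol gives no number of men uncleared at Year 5. The 28.6% is therefore calendar time without a reporting duty and does not measure time at risk.

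Third, at most 15 men are dosed (14.7), and the safety analysis in 14.6 describes no pregnancy rate. Two more years would yield individual case reports and no usable rate. That limits the statistical value, but a complete count of pregnancies is still needed to put any abnormal outcome in context.

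Fourth, on the inhibitor item, a reader might infer that a positive result in Years 6-7 would wait 26 weeks for repeat testing. The documents do not support that. Inhibitor development must be reported within 24 hours at any time (10.2.1), clinically significant results may be repeated at the investigator's discretion (9.7.9.2), and extra FVIII testing is allowed after discussion with the Medical Monitor (Table 9.1.5, footnote b). Twenty-six weeks is the visit interval only.

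**Conclusion.** The inconsistency is real and lies in the current text. Required partner-pregnancy reporting stops at 5 years, while AE/SAE reporting, safety follow-up and any outstanding semen testing run to about 7, with no reason stated. The gap is 104 of 364 post-infusion weeks (28.6%), taking a protocol year as 52 weeks, as the visit schedule does. The loss is the count of pregnancies and their normal outcomes. It does not extend to abortions or congenital anomalies.

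The point should be corrected because safety is a primary objective and the change is cheap. It does not touch the efficacy analysis. The Bethesda footnote is a separate, minor matter of consistency and adds nothing to the size of this one.

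**What to change.** - Amend 10.4.1.9 so that partner pregnancies are reported and followed to outcome over the same period as adverse events in 10.3.1, through Week 364. If the sponsor wants a shorter window, the section should give the reason.
- Add a pregnancy question to the Year 6-7 remote contacts and site visits (12.9.1, 12.9.2).
- Ask sites to report retrospectively, on the existing Pregnancy eCRF, any partner pregnancy since Year 5.
- Separately, reconcile the Years 3-5 limit in footnotes c and d of Table 9.1.5 with the Year 6-7 Bethesda schedule.

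The cost is a small reporting burden in at most 15 subjects, the partner's consent where an outcome is followed, and ethics committee review of the amendment. If the consent form has to change, approval is needed before the change takes effect (14.9).

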10.5 Reporting Requirements

10.5.1 Expedited Reporting Requirements

All SAEs and EOSI that occur during the course of the AE Reporting Period (refer to Section 10.3.1), whether or not considered related to study drug, must be reported by entering the information in the AE eCRF and submitting to BPV within 24 hours of the site becoming aware of the event. Investigators should not wait to collect information that fully documents the event before notifying BPV of an SAE. BioMarin may be required to report certain SAEs to regulatory authorities within 7 calendar days of being notified about the event; therefore, it is important that Investigators submit any information requested by BioMarin as soon as it becomes available.

The Sponsor is responsible for identifying, preparing and reporting all SUSARs to the relevant competent authorities, ethics committees and investigators in accordance with the requirements identified in the Clinical Trials Regulations.

If the EDC is unavailable, all SAEs should be reported to BPV by completing the SAE Report Form and faxing or emailing the completed form to BPV within 24 hours of the site becoming aware of the event. Once the EDC is available, the information should be entered in the AE eCRF.

10.5.2 Ethics Committee Reporting Requirements

Reporting of SAEs to the Independent Ethics Committee (IEC) will be done in compliance with the standard operating procedures and policies of the IEC and with applicable regulatory requirements. Adequate documentation must be obtained by BioMarin showing that the IEC was properly and promptly notified as required. Proprietary and Confidential 24 August 2021

BOMARIN[®] 270-201

10.6 Follow-up of Subjects after Adverse Events

The Investigator should follow all unresolved AEs and SAEs until the events are resolved or have stabilized, the subject is lost to follow-up, or it has been determined that the study treatment or participation is not the cause of the AE/SAE. Resolution of AEs and SAEs (with dates) should be documented on the AE eCRF and submitted to BioMarin Pharmacovigilance and in the subject's medical record to facilitate source data verification.

For some SAEs, the Sponsor may follow up by telephone, fax, electronic mail, and/or a monitoring visit to obtain additional case details (eg, hospital discharge summary, consultant report, or autopsy report) deemed necessary to appropriately evaluate the SAE report.

10.7 Post-Study Adverse Events

At the last scheduled visit, the Investigator should instruct each subject to report, to the Investigator and/or to BPV directly, any subsequent SAEs that the subject's personal physician(s) believes might be related to prior study treatment.

The Investigator should notify the study Sponsor of any death or SAE occurring at any time after a subject has discontinued or terminated study participation, if the Investigator believes that the death or SAE may have been related to prior study treatment. The Sponsor should also be notified if the Investigator should become aware of the development of cancer or of a congenital anomaly in a subsequently conceived offspring of a subject that participated in this study.

10.8 Urgent Safety Measures

The regulations governing clinical trials state that the Sponsor and Investigator are required to take appropriate urgent safety measures to protect subjects against any immediate hazards that may affect the safety of subjects, and that the appropriate regulatory bodies should be notified according to their respective regulations. According to the European Union (EU) Clinical Trial Directive 2001/20/EC, "…in the light of the circumstances, notably the occurrence of any new event relating to the conduct of the trial or the development of the investigational medicinal product where that new event is likely to affect the safety of the patients, the Sponsor and the Investigator shall take appropriate urgent safety measures to protect the patients against any immediate hazard. The Sponsor shall forthwith inform the competent authorities of those new events and the measures taken and shall ensure that the IEC is notified at the same time."

The reporting period for these events which may require the implementation of urgent safety measures is the period from the time of signing of the ICF through the completion of the last study visit or at the Early Termination Visit (ETV). Investigators are required to report any

Proprietary and Confidential

BIOMARIN[®] 270-201 Amendment 10

events which may require the implementation of urgent safety measures to BioMarin within 24 hours of becoming aware of the event.

Examples of situations that may require urgent safety measures include discovery of the following:

- Immediate need to revise the IP administration (eg, modified dose amount or frequency not defined in protocol)
- Lack of study scientific value, or detrimental study conduct or management
- Discovery that the quality or safety of the IP does not meet established safety requirements

11 APPROPRIATENESS OF MEASUREMENTS

The measures of efficacy to be used in this study are standard, ie, widely used and generally recognized as reliable, accurate, and relevant (able to discriminate between effective and ineffective agents). The measures of safety used in this study are routine clinical and laboratory procedures.

The chromogenic substrate assay and the one-stage clotting assay are both validated and utilize CE marked reagents. The exploratory FVIII activity assay will be used for exploratory purposes only.

